#### **4. ANALYSIS POPULATIONS**

In this study, four analysis populations are defined: Intention-to-treat (ITT), Safety, Pharmacokinetic and the Per Protocol populations (PP).

Furthermore, any additional exploratory analysis not identified in the SAP will be identified in the final CSR as exploratory post hoc analyses. This may include the addition of additional study populations or subgroups of interest.

The number and percentage of subjects in each analysis population will be summarized.

##### **4.1 Population Descriptions**

###### ***4.1.1 Intention-to-treat (ITT) population***

The ITT population will be defined as all randomized subjects. Subjects will be analyzed per the randomized treatment they received if different from the actual treatment received.

All disposition, demographic and pharmacodynamic (PD) analyses will be based on the ITT population. All listings will be presented by the ITT population.

###### ***4.1.2 Safety population***

The safety population will be defined as all enrolled subjects who received at least one dose of the study drug and will be based on actual treatment received.

If the safety population differs from the ITT population in that subjects received a different treatment to that they were randomized, or did not receive treatment whatsoever after randomization, the demographic and pharmacodynamic analyses will be repeated for the safety population.

All safety analyses will be based on the safety population.

###### ***4.1.3 Pharmacokinetic (PK) population***

The PK population will comprise all subjects in the safety population who provide adequate PK samples to calculate the PK parameters. Subjects with important protocol deviations will be assessed on a subject-by-subject basis for inclusion in the PK Population. The PK analysis will be conducted using the Pharmacokinetic population.

###### ***4.1.4 Per Protocol (PP) population***

The PP population will comprise all subjects in the safety population excluding subjects who missed doses and/or randomly discontinued the study before the primary Day 7 Visit. Furthermore, subject that had any relevant important protocol deviations will be excluded from the PP population.

## 5. PROTOCOL DEVIATIONS

In case protocol deviations/violations are reported, all protocol deviations/violations will be listed for each subject in the by-subject data listings. Prior to database lock and during the blinded review of database, all protocol deviations/violations will be reviewed and assigned a status of important or not.

Important protocol deviations/violations may include the following, depending on the timing and nature of the deviation:

- **INFORMED CONSENT DEVIATION:** Subject not consented prior to study procedures being performed or subject not re-consented to study at next scheduled study visit following local approval of an updated PIS-CF.
- **ENTRY DEVIATION:** Subject enrolled in violation of eligibility criteria.
- **WITHDRAWAL DEVIATION:** Subject developed withdrawal criteria during the study, but were not withdrawn.
- **DOSING DEVIATION:** Subject received the wrong treatment or incorrect dose of investigational product or comparator; Subject received treatment at incorrect timepoint in study; Subject received treatment that had not been stored per protocol.
- **OPERATIONAL DEVIATION:** Informed consent deviations (other than consent not being obtained prior to study entry, which would be considered an Entry Deviation), IRB/IEC expired approval, significant visit window deviations, or other issues that may significantly impact subject safety or data integrity.

## **6. SUBJECT DISPOSITION**

Outcomes will be summarized by the treatment groups as specified in section 3.

### ***6.1.1 Subject disposition***

Subject disposition will be summarized using counts and percentages and will be based on the ITT Population. The number of screened subjects, number and percentage of randomized subjects, subjects discontinued from the study as well as the primary reason for discontinuation will also be summarized.

All disposition information collected will be listed together with the date that the subject provided informed consent and the date and time of the first study drug administration.

If there is a difference between the ITT, Safety populations or the PP population, the disposition summary tables will be repeated for that population.

### ***6.1.2 Analysis Populations***

The number of subjects included in each of the defined analysis populations will be summarized using counts and percentages and will be based on the ITT Population.

In addition, the inclusion/exclusion of each subject into/from each of the defined analysis populations will be listed.

## **7. DEMOGRAPHIC AND BASELINE INFORMATION**

Demographic and baseline body measurements will be summarized using the ITT Population and may be repeated for the safety population and per protocol populations if different from the ITT population.

All information will be presented by the treatment groups as specified in section 3.

### **7.1 Demographics**

#### **7.1.1 Definition of variables**

- Age (years);
- Sex;
- Child Bearing Potential;
- Method of Birth Control;
- Race;
- Height (cm);
- Weight (kg);

#### **7.1.2 Biostatistical methods**

Quantitative and categorical summaries will be presented for demographic variables at the screening visit.

A by-subject data listing for demographic and baseline characteristics will be generated.

### **7.2 Medical history**

Past medical history will be coded using the Medical Dictionary for Regulatory Activities, (MedDRA - latest version), and will be presented in the by-subject data listings including the MedDRA codes.

### **7.3 Pregnancy Test (Serum and Urine)**

Pregnancy test results will be included in the by-subject data listings. This includes the pregnancy test results at Screening and Day 28/End of Study.

### **7.4 Serology**

The following viral detection results (serologies) at Screening will be listed for each subject when available: Hepatitis B, Hepatitis C and HIV status.

### **7.5 Other baseline characteristics**

Confirmation of CAP (both clinical and radiographic) will be presented in the by-subject data listings.

## **8. STUDY DRUG ADMINISTRATION**

Study drug administration results will be presented using the ITT Population.

A by-subject data listing will be generated for study medication administration. These listings will include randomized dose assignment, Date/Time of Injection, Study Drug Administered (mL), duration of administrations, reason whole study drug dose was not administered, injection interruptions, re-start and reason for any interruptions. Subjects who receive the wrong IP (rhu-pGSN vs. placebo) will be flagged.

## 9. PHARMACOKINETICS (PK)

All PK summary tables and figures will be based on the PK Population. All listings will be based on the Safety Population (Actual Treatment). All analyses will be done by treatment group.

For the 1 dose in the SD arm and the first 2 doses in the MAD arms, blood will be drawn within 30 minutes pre-dose, and 5-10 minutes after the end of administration, as well as 2, 8, 12 and/or 16, and 24 hours after the end of administration ( $\pm$  30 minutes) for analysis. Identical PK sampling is encouraged on Day 3 where feasible (but not required) in the multiple-dose arms.

In this section (section 9):

- The rhu-pGSN treatment group will be referred to the Active treatment group.
- Exogenous pGSN concentrations will be referred to as rhu-pGSN concentrations.
- Endogenous pGSN + Exogenous pGSN (total) will be referred to as pGSN

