5.2.2. Secondary Endpoints

- PK for rhu-pGSN including, but not limited to maximum concentration (C_{max}), time to maximum concentration (T_{max}), terminal half-life ($T_{1/2}$), area under the curve from time zero to 8 hours (AUC_{0-8}), area under the curve from time zero to infinity (AUC_{inf}) (levels measured within 30 minutes predose, 5-10 minutes after the end of administration, and 2, 8, 12 and/or 16, and 24 hours (\pm 30 minutes) after each dose (Day 3 sampling in multiple-dose arms is optional)

- Incidence, causality, and severity of AEs and SAEs graded according to the NCI CTCAE version 4.03 (or equivalent); clinically significant laboratory and/or EKG abnormalities as required by SOC; death irrespective of cause; cause of death per investigator, including relationship to study drug; use of vasopressors, intubation, or transfer to the ICU or equivalent through Day 28 (secondary time point)

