6.3. Doses and Schedule of Administration

In the SD arm, subjects will receive one dose of rhu-pGSN or placebo on Day 1 as an IV push at 6 mg/kg.

In the MAD arms, subjects will receive once-daily doses approximately 24 hours apart of rhu-pGSN or placebo on Days 1 through 3 as an IV push at 6, 12, or 24 mg/kg. The first 2 doses

must be administered in the hospital, but the third dose can be given in a monitored outpatient setting where appropriate.

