### 9.1 Definition of variables

The following PK parameters for pGSN will be estimated For Day 1(SD/MAD), Day 2 (MAD) and Day 3 (MAD). PK Parameters will only be calculated for the Active (rhu-pGSN) treatment group. No PK parameters will be calculated for the Placebo treatment group:

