	Maximum	x	x	x	
	CV%	x.x	x.x	x.x	
	BLQ	x (xx.x%)	x (xx.x%)	x (xx.x%)	

SD: Standard Deviation; BLQ: Below Limit of Quantification

Clinical cut-off date: DDMMYYYY

Program: filepath\_name, Output: filepath\_name (version x.x) Created: DDMMYYYY HH:MM

Programming Note: Repeat for all timepoints.

Table 14.2.1.5 Day 2: Summary of Estimated Plasma rhu-pGGSN Concentrations (unit) by Timepoint (continued)  
 Protocol: BTI-201  
 PK Population

Time Point	MAD rhu-pGGSN 24 mg/kg (N=xx)	Actual Value	Change from Pre-Injection	(Change from Pre-Injection) - (Mean Placebo Change from Pre- Injection)	Actual Value	Change from Pre-Injection
Pre-Injection		n x x.x x.x x.x x x x.x x (xx.x%)			x x.x x.x x.x x x x.x x (xx.x%)	
5 to 10 mins post		n Mean SD Minimum Maximum CV% BLQ	x x.x x.x x.x x x x.x x (xx.x%)		x x.x x.x x.x x x x.x x (xx.x%)	x x.x x.x x.x x x x.x x (xx.x%)

SD: Standard Deviation; GeoMean: Geometric Mean; GeoCV%: Geometric CV%; BLQ: Below Limit of Quantification

Clinical cut-off date: DDMMYYYY  
 Program: filepath\_name, Output: filepath\_name (version x.x) Created: DDMMYYYY HH:MM

Programming Note: Repeat for all timepoints.

Table 14.2.1.6 Day 3: Summary of Estimated Plasma rhu-pGSN Concentrations (unit) by Timepoint  
Protocol: BTI-201  
PK Population

Programming Note: Repeat Table 14.2.1.5 for Day 3.

Table 14.2.2.1 Day 1: Summary of Plasma pGSN PK Parameters  
 Protocol: BTI-201  
 PK Population

Parameter (unit)	SD/MAD rhu-pGSN 6 mg/kg (N=xx)	MAD rhu-pGSN 12 mg/kg (N=xx)	MAD rhu-pGSN 24 mg/kg (N=xx)	Placebo (N=xx)
AUC 0-t (unit)				
n	x	x	x	x
Mean	x.x	x.x	x.x	x.x
SD	x.x	x.x	x.x	x.x
Minimum	x.x	x.x	x.x	x.x
Median	x	x	x	x
Maximum	x	x	x	x
CV%	x.x	x.x	x.x	x.x
GeoMean	x.x	x.x	x.x	x.x
GeoCV%	x.x	x.x	x.x	x.x
C max (unit)				
n	x	x	x	x
Mean	x.x	x.x	x.x	x.x
SD	x.x	x.x	x.x	x.x
Minimum	x.x	x.x	x.x	x.x
Median	x	x	x	x
Maximum	x	x	x	x
CV%	x.x	x.x	x.x	x.x
GeoMean	x.x	x.x	x.x	x.x
GeoCV%	x.x	x.x	x.x	x.x

SD: Standard Deviation; GeoMean: Geometric Mean; GeoCV%: Geometric CV%

Clinical cut-off date: DDMMYYYY  
 Program: filepath\_name, Output: filepath\_name (version x.x) Created: DDMMYYYY HH:MM

Programming Note: Repeat for all PK parameters.

Table 14.2.2.2 Day 2: Summary of Plasma pGSN PK Parameters  
 Protocol: BTI-201  
 PK Population

Parameter (unit)	MAD rhu-pGSN 6 mg/kg (N=xx)	MAD rhu-pGSN 12 mg/kg (N=xx)	MAD rhu-pGSN 24 mg/kg (N=xx)	Placebo (N=xx)
AUC 0-t (unit)				
n	x	x	x	x
Mean	x.x	x.x	x.x	x.x
SD	x.x	x.x	x.x	x.x

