## GENERAL COMMENTS

- Names of Treatment Groups:  
SD:
  - rhu-pGSN 6 mg/kg.
- MAD:
  - rhu-pGSN 6 mg/kg;
  - rhu-pGSN 12 mg/kg;
  - rhu-pGSN 24 mg/kg.
- Names of PK sampling times:  
Day 1 (SD and MAD) & Day 3 (MAD)
  - Pre-injection
  - 5 to 10 mins
  - 2h
  - 8h
  - 12h
  - 16h
  - 24h

Figure 14.2.1.1 Individual pGSN Plasma Concentrations (ng/mL) (Linear scale) by Day  
Protocol: BTI-201  
PK Populations

Day 1

Programming Note:

The x-axis will represent the actual study time in hours (0 – 24 hours).

The y-axis will represent the pGSN Plasma Concentrations (ng/mL). The y-axis will be on the linear scale.

All subjects will be represented on a single page. Each dose level will be presented as a distinct line type. A separate figure will be created for each Day. SD and MAD subjects will be presented on the same page by Day.

Clinical cut-off date: DDMMYYYY  
Program: filepath\_name, Output: filepath\_name (version x.x) Created: DDMMYYYY HH:MM

Figure 14.2.1.2 Individual pGSN Plasma Concentrations (ng/mL) (Semi-logarithmic) by Day  
Protocol: BTI-201  
PK Populations

Day 1

Programming Note:

The x-axis will represent the actual study time in hours (0 – 24 hours).

The y-axis will represent the pGSN Plasma Concentrations (ng/mL). The y-axis will be on the log scale.

All subjects will be represented on a single page. Each dose level will be presented as a distinct line type. A separate figure will be created for each Day. SD and MAD subjects will be presented on the same page by Day.

Clinical cut-off date: DDMMYYYY  
Program: filepath\_name, Output: filepath\_name (version x.x) Created: DDMMYYYY HH:MM

Figure 14.2.2.1 Individual Estimated Plasma rhu-pGSN Plasma Concentrations (ng/mL) based on Changes from Pre-Injection (Linear scale) by Day

Protocol: BTI-201  
PK Populations

Day 1

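### Repeat-dose PK is planned only as separate daily group summaries, and the subjects behind them change from Day 1 to Day 2 at 6 mg/kg and can change on Day 3 at every dose

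*SAP*

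**What the plan says.** **Sampling.** SAP section 9 makes two dosing days compulsory: "For the 1 dose in the SD arm and the first 2 doses in the MAD arms, blood will be drawn". For the third dose, "Identical PK sampling is encouraged on Day 3 where feasible (but not required) in the multiple-dose arms". The protocol agrees: under Secondary Endpoints (5.2.2), "Day 3 sampling in multiple-dose arms is optional". Protocol 6.3 adds that "the third dose can be given in a monitored outpatient setting where appropriate".

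**Analysis.** SAP 9.1 nevertheless calls for PK parameters on Day 1 (SD and MAD), Day 2 (MAD) and Day 3 (MAD). SAP section 17 lists a separate table for each day: 14.2.1.x for concentrations, 14.2.2.x for pGSN parameters and 14.2.3.x for estimated rhu-pGSN parameters. In the Day 1 parameter shell, the lowest-dose column is headed "SD/MAD rhu-pGSN 6 mg/kg (N=xx", one pooled group. The Day 2 and Day 3 shells are MAD only. SAP section 3 exempts PK summaries from the SD/MAD split applied elsewhere, so the pooling is deliberate.

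**Population and missing data.** In SAP 4.1.3, "The PK population will comprise all subjects in the safety population who provide adequate PK samples to calculate the PK parameters". The rule is not set by day and does not ask for data on every day. Section 14 promises imputation of missing PK points and refers to section 9, which covers only values below the quantitation limit, not an unsampled Day 3 profile.

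**Between-day measures.** The parameter list in 9.1 has no accumulation ratio, and 9.2 has no within-subject comparison of Cmax or AUC across days.

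**The concern.** The secondary objective is the PK profile after single or multiple doses. With only daily group summaries available, a reader looking for accumulation or time-dependent kinetics will set the Day 1, Day 2 and Day 3 means side by side. Where different people stand behind those means, a rise or fall can come from repeat dosing, from the change of people, or from both.

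There are two sources of change. At 6 mg/kg half of the Day 1 column comes from the single-dose cohort and cannot appear on Day 2. Cohorts are filled sequentially, so SD and MAD subjects are not randomised against each other. On Day 3, at every dose, who gives a profile depends on feasibility, and the third dose may be given after discharge. The MAD subjects already supply Day 1 and Day 2 profiles from the same people, but the SAP specifies no summary that uses this pairing.

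**Working it through.** **1. Planned denominators.** Protocol 7.1 gives 6 active and 2 placebo per cohort in 4 cohorts: (6 + 2) × 4 = 32, the stated total. No PK sample-size or precision figure is given to reproduce. Planned active subjects by day, before any replacement under Protocol 6.10, are:

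| Dose | Day 1 | Day 2 | Day 3 |
|---|---|---|---|
| 6 mg/kg | 6 SD + 6 MAD = 12 | 6 | 0 to 6 |
| 12 mg/kg | 6 | 6 | 0 to 6 |
| 24 mg/kg | 6 | 6 | 0 to 6 |

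At most 6/12 = 50% of the Day 1 column at 6 mg/kg can reappear on Day 2. Of the six adjacent-day steps (3 doses × 2), four can involve different subjects: Day 1 to 2 at 6 mg/kg, and Day 2 to 3 at each dose if fewer than 6 are sampled. Day 1 to 2 at 12 and 24 mg/kg cannot. Combined placebo, if pooled the same way, goes from 8 to 6 between Day 1 and Day 2, so the double-delta reference changes too.

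**2. Assumptions for size.** The documents give no PK variability. Assume log-normal exposure, between-subject CV 30% to 50%, within-subject CV 15% and no true change between days. Log variance is ln(1 + CV²): sb² = 0.0862 (30%) or 0.2231 (50%), and sw² = 0.0223 (15%).

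**3. Day 2/Day 1 at 6 mg/kg, sampling complete.** The pooled comparison leaves a between-subject term, (mean MAD − mean SD)/2, with variance sb²/12.
- That term alone gives a 95% range for the ratio of 0.85–1.18 (CV 30%) or 0.77–1.31 (CV 50%).
- An assumed 1.25-fold difference between the SD and MAD cohorts moves the ratio to √(1/1.25) = 0.89 or √1.25 = 1.12.
- Adding within-subject error, the log variance is sb²/12 + sw²/4, a 95% range of ×/÷1.25 to 1.36. Paired in the 6 MAD subjects it is sw²/3, or ×/÷1.18.

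**4. Day 3/Day 1 with 3 of 6 sampled at random.**
- Against all 6 MAD subjects: sb²(1/3 − 1/6) + sw²(1/3 + 1/6), giving ×/÷1.37 to 1.54.
- Against the pooled 12 at 6 mg/kg: sb²(1/3 − 1/12) + sw²(1/3 + 1/12), giving ×/÷1.41 to 1.65.
- Paired in the 3 sampled: 2sw²/3, giving ×/÷1.27.

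**5. Day 3/Day 1 if sampling is selective.** If selection correlates 0.5 with exposure, the log shift against all 6 MAD subjects is 0.5 × sb × the mean of the k largest (or smallest) of six standard normal values, about 0.70 for k = 3 and 0.95 for k = 2 in size.

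| Sampled | Selected for lower exposure | Selected for higher exposure |
|---|---|---|
| 3 of 6 | 0.90 to 0.85 | 1.11 to 1.18 |
| 2 of 6 | 0.87 to 0.80 | 1.15 to 1.25 |

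Each pair runs from CV 30% to CV 50%. The paired ratio stays at 1.00 only if selection is unrelated to a subject's own day-to-day change.

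**6. When pairing improves precision.** Setting sb²/12 + sw²/4 against sw²/3, and sb²/6 + sw²/2 against 2sw²/3, gives the same condition: pairing is tighter only if sb exceeds sw. With both CVs at 30% the two methods tie, at ×/÷1.39 for step 3 and ×/÷1.60 for step 4 (against all 6). With within-subject CV 40% and between-subject 30%, pairing is slightly wider: 1.55 against 1.51, and 1.85 against 1.79.

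**The case against.** The best defence is that these are descriptive tables, one per day, with no trend test or accumulation parameter promised. No error rate is affected. That stands, and it limits the grade of the point.

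Much of the raw material is also in the plan. By-subject MAD parameters are listed by day (16.2.6.3.2 and 16.2.6.4.2), and individual profiles are plotted by day. The shells print n, so a thin Day 3 will show. Protocol Table 6 requires the 24-hour sample before the next dose, so the levels before doses 2 and 3 are planned for all MAD subjects. SAP section 3 mentions a ratio to the Day 1 pre-dose concentration, and the MAD concentration listing has a column for it, although 9.2 uses each day's own pre-dose value. A paired analysis can therefore be recovered. What is missing is a prespecified summary of Cmax and AUC, without which any such analysis is post hoc.

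Pooling is sensible for Day 1 itself, because both groups have then had one 6 mg/kg dose. The difficulty arises only when that column is read against Day 2 or Day 3.

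A reader might infer that subjects sampled on Day 3 are the sicker ones, so Day 3 exposure is biased downward. The documents do not say so. Protocol 4.3 links falling pGSN to mortality in other conditions, not to exposure after dosing in CAP. The change-from-pre-dose and double-delta parameters also subtract the pre-dose level, which should weaken that route.

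**Conclusion.** The point holds as an inexpensive improvement to a descriptive analysis. The change of subjects is built in for Day 1 to Day 2 at 6 mg/kg. It is possible for Day 3 at every dose and absent for Day 1 to Day 2 at 12 and 24 mg/kg. Two things are certain from the documents: the 12, 6, 0-to-6 pattern at 6 mg/kg, and the lack of any defined between-day Cmax or AUC ratio. The numerical sizes rest on assumed CVs. The Day 3 shifts also rest on an assumed correlation of 0.5, their sign is unknown, and they disappear if all 6 are sampled.

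Four stronger readings are not supported. The documents do not show that every day-to-day comparison is confounded, since two of the three Day 1 to Day 2 steps use the same planned subjects. Pairing is not more precise regardless of variability: that needs between-subject to exceed within-subject variability, and neither is given. No passage ties the Phase 2b/3 dose to a between-day PK trend. Finally, the figure shells' sampling-time list names Day 1 and Day 3 but not Day 2; this is clerical, because the same shells call for a figure for each day and the Day 2 tables are listed.

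**What to change.** In SAP 9.2 and the PK table shells:

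1. Add descriptive within-subject ratios in MAD subjects with both days, by dose, for Cmax, AUC0-8, AUC over 24 hours and pre-dose level. Report the geometric mean ratio, 90% CI and n. Make Day 2/Day 1 the main comparison, because both days are compulsory. Label Day 3/Day 1 as restricted to subjects sampled on Day 3.
2. In the Day 1 tables, show MAD 6 mg/kg in its own column as well as the pooled SD/MAD column.

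Add Day 2 to the figure-shell sampling-time list as a clerical correction.

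The cost is some SAP wording and a few extra columns. No new samples or visits are needed. The one downside is that a small Day 3 n will be plainly visible.

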### 9.1 Definition of variables

The following PK parameters for pGSN will be estimated For Day 1(SD/MAD), Day 2 (MAD) and Day 3 (MAD). PK Parameters will only be calculated for the Active (rhu-pGSN) treatment group. No PK parameters will be calculated for the Placebo treatment group:

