5.1.2. Secondary Objectives

- To characterize the PK profile of rhu-pGSN after single or multiple IV doses

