11.4.3. Pharmacokinetics and Immunogenicity

To complete the PK analyses, plasma specimens will be periodically sampled relative to study drug administration and stored frozen for pGSN measurements. For the 1 dose in the SD arm and the first 2 doses in the MAD arms, blood will be drawn within 30 minutes predose, and 5-10 minutes after the end of administration, as well as 2, 8, 12 and/or 16, and 24 hours after the end of administration (± 30 minutes) for analysis of C_{max} , $T_{1/2}$, AUC_{0-8h} , and AUC_{inf} . Identical PK sampling is encouraged on Day 3 where feasible (but not required) in the multiple-dose arms.

Immunogenicity will be assessed at the last visit on Day 28 ± 2 days. Antibodies against rhu-pGSN will be assayed from frozen specimens to determine whether the investigational product induces an antibody response in recipients.

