#### **Day 1: SD/MAD & Day 2/3: MAD**

AUC 0-t	The area under the plasma concentration-time curve, from time 0 (time of dosing) to the last time point (24 hours) with measurable analyte concentration, calculated by the log down, linear up trapezoidal method.  AUC 0-t will additionally be calculated for the estimated rhu-pGSN profile for both the change from pre-dose on each study day and the double-delta method.
AUC 0-8	The area under the plasma concentration-time curve, from time 0 (time of dosing) to the 8 hours concentration, calculated by the log down, linear up trapezoidal method.  AUC 0-8 will additionally be calculated for the estimated rhu-pGSN profile for both the change from pre-dose on each study day and the double-delta method.
AUC 0-inf	The area under the plasma concentration-time curve from time 0 extrapolated to infinity. AUC 0-inf is calculated as the sum of AUC 0-t plus the ratio of the last measurable plasma concentration to the elimination rate constant ( $k_{el}$ ).
C max	Maximum observed concentration.  C max will additionally be calculated for the estimated rhu-pGSN profile for both the change from pre-dose on each study day and the double-delta method.
T max	Time to maximum observed drug concentration. If the maximum value occurs at more than one time point, T max is defined as the first time point with this value.

$k_{el}$	Apparent terminal elimination rate constant calculated by linear regression of the terminal linear portion of the log concentration vs. time curve.
$t_{1/2}$	Apparent elimination half-life, calculated as $\ln(2)/k_{el}$
%AUC ext	Percentage of the extrapolated area under the plasma concentration-time curve, calculated as $100\% * [AUC_{0-inf} - AUC_{0-t}] / AUC_{0-inf}$
$C_L/F$	Apparent clearance calculated as $Dose/AUC_{0-inf}$ .
$V_z/F$	Apparent volume of distribution at the terminal phase, calculated as $Dose / (k_{el} \times AUC_{0-inf})$ .
DN_C max	Dose-normalized C max , calculated as C max divided by dose DN_C max will additionally be calculated for the estimated rhu-pGSN profile for both the change from pre-dose day 1 and the double-delta method..
DN_AUC 0-inf	Dose-normalized AUC 0-inf , calculated as AUC 0-inf divided by dose

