#### Analysis of Estimated rhu-pGSN

This analysis will exclude the placebo treatment group:

- Pre-dose values on each study day will be presented as recorded;
- Pre-dose values on each study day that are BLQ will be set to  $\frac{1}{2}$  LLQ;
- Subsequent BLQ values (post the first quantifiable concentration on each day) will be set to  $\frac{1}{2}$  LLQ.
- Estimated rhu-pGSN concentration  
= concentration on Day z at Time Point y – Day z Pre-dose concentration

Individual estimated rhu-pGSN concentrations will be summarized by nominal sampling time. Geometric summary statistics will not be calculated for estimated rhu-pGSN concentrations, as these values could be lower than or equal to 0.

Estimated Individual (for each subject) and mean estimated plasma rhu-pGSN concentration over time will be displayed graphically in linear plots of estimated rhu-pGSN concentration versus time. The actual collection time will be used for individual estimated plasma rhu-pGSN concentration curve and the nominal time will be used for plot of mean estimated plasma rhu-pGSN concentration curve.

Estimated plasma concentrations vs. time data will be analyzed using SAS software. Actual collection time will be used in the calculation of plasma PK parameters. The following parameters (including dose normalized parameters) will be calculated for each study day:

- $AUC_{0-t}$
- $AUC_{0-8h}$
- $C_{max}$

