#### Double Delta Analysis of Estimated rhu-pGSN

- Pre-dose values on each study day will be presented as recorded;
- Pre-dose values on each study day that are BLQ will be set to  $\frac{1}{2}$  LLQ;
- Subsequent BLQ values (post the first quantifiable concentration on each day) will be set to  $\frac{1}{2}$  LLQ.
- Estimated rhu-pGSN will be calculated as follows:  
= (Active Treatment Group Concentration on Day z at Time Point y – Day z Pre-dose Concentration) - (Mean Placebo Treatment Group Concentration on Day z at Time Point y – Mean Placebo Day z Pre-dose Concentration)

Estimated rhu-pGSN concentrations will be summarized by nominal sampling time. Geometric summary statistics will not be calculated for estimated rhu-pGSN concentrations, as these values could be lower than or equal to 0.

Estimated Individual (for each subject) and mean estimated plasma rhu-pGSN concentration over time will be displayed graphically in linear plots of estimated rhu-pGSN concentration versus time. The nominal time will be used for individual estimated plasma rhu-pGSN concentration curve and the nominal time will be used for plot of mean estimated plasma rhu-pGSN concentration curve.

Estimated rhu-pGSN plasma concentrations vs. time data will be analyzed using SAS software. Nominal time will be used in the calculation of plasma PK parameters. The following parameters (including dose normalized parameters) will be calculated for each study day:

- $AUC_{0-t}$
- $AUC_{0-8h}$
- $C_{max}$

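### Half-life, AUCinf and the parameters derived from them are planned only on total (endogenous plus exogenous) pGSN, although the protocol's secondary PK endpoints are for rhu-pGSN

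*SAP*

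**What the plan says.** Protocol 5.1.2 gives the secondary objective: "To characterize the PK profile of rhu-pGSN after single or multiple IV doses". Protocol 5.2.2 lists the endpoints as "PK for rhu-pGSN including, but not limited to maximum concentration", followed by Tmax, T1/2, AUC0-8 and AUCinf. SAP 2.2.2 repeats the objective for rhu-pGSN.

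SAP 9 separates the two analytes. Exogenous protein is called rhu-pGSN, while "Endogenous pGSN + Exogenous pGSN (total) will be referred to as pGSN". SAP 9.1 then states: "The following PK parameters for pGSN will be estimated For Day 1(SD/MAD), Day 2 (MAD) and Day 3 (MAD". It lists 14 parameters:

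- **With a rhu-pGSN version (6):** Cmax, AUC0-t, AUC0-8 and their dose-normalised forms, each by change from pre-dose and by double-delta.
- **On total pGSN only (8):** AUC0-inf, Tmax, k_el, t1/2, %AUCext, CL/F, Vz/F and DN_AUC0-inf.

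k_el is defined as: "Apparent terminal elimination rate constant calculated by linear regression of the terminal linear portion of the log concentration vs. time curve".

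In SAP 9.2, both rhu-pGSN analyses introduce their lists with "The following parameters (including dose normalized parameters) will be calculated for each study day" and name only AUC0-t, AUC0-8h and Cmax. Mock Tables 14.2.3.1-14.2.3.3 and Listings 16.2.6.4.1-16.2.6.4.2 match. Half-life, AUC0-inf and clearance have columns only in the pGSN Listings 16.2.6.3.1-16.2.6.3.2. SAP 15 declares no change from the planned analysis.

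**The concern.** Two named secondary endpoints, T1/2 and AUCinf, have no planned estimate for the analyte the protocol names. Total pGSN cannot stand in for it. After the dose, total pGSN falls towards the patient's own endogenous level and not towards zero, so its log slope understates the elimination rate of the drug. C_last/k_el then adds endogenous protein to the extrapolated area, and CL/F, Vz/F and DN_AUC0-inf inherit the error. Because the endogenous share is largest at 6 mg/kg, a drug with linear kinetics would appear non-linear across 6, 12 and 24 mg/kg in these parameters.

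The corrected profiles cannot simply be extended to Days 2 and 3. Both subtract that day's pre-dose value (SAP 3, baseline definition; SAP 9.2), which after the first dose contains residual drug. The placebo term in the double-delta does not put it back.

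**Working it through.** The plan states no figure to reproduce. The gap itself is textual; the arithmetic below only shows direction and possible size.

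**Inputs from the documents.** Doses of 6, 12 and 24 mg/kg. Samples at pre-dose, 5-10 minutes, 2, 8, 12 and/or 16, and 24 h (Protocol 9.3). Normal endogenous level 200-300 mg/L, falling in illness (Protocol 4.3).

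**Assumed inputs, not in the documents.** Volume V 0.045, 0.06 or 0.1 L/kg; true half-life 8, 12 or 24 h; patient baseline B 50, 100, 150 or 200 mg/L, constant; fitting window 8-24 h, repeated with 12-24 h.

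**Direction.** With total C(t) = B + A·exp(-kt) and A = dose/V, the slope of log C is -k multiplied by the drug's share of the total. Take B = 100, V = 0.045, half-life 12 h and 6 mg/kg, so A = 133.3 mg/L. At 12 h the drug is 66.7 of 166.7 mg/L, a share of 0.40, and the local half-life is 12/0.40 = 30 h. At 24 mg/kg the share at 12 h is 266.7/366.7 = 0.727, giving 16.5 h.

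**Worked example, 8-24 h fit, same inputs.** At 6 mg/kg the fitted half-life is 34.8 h. AUC0-24 is about 4,130 mg·h/L. The extrapolated part is 133.3 × 34.8/ln 2, about 6,700. AUC0-inf is about 10,830, against a true drug value of 133.3 × 12/ln 2 = 2,308. CL is therefore 21% of truth.

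| Dose (mg/kg) | Apparent half-life (true 12 h) | CL, % of truth | AUC0-inf/dose (true 385) |
|---|---|---|---|
| 6 | 35 h | 21 | 1,805 |
| 12 | 24 h | 40 | 960 |
| 24 | 18 h | 60 | 638 |

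Subtracting the Day 1 pre-dose value returns 12.0 h and 100% of CL when the baseline is constant.

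**Whole grid, 8-24 h fit.**

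| Dose (mg/kg) | Apparent/true half-life | CL, % of truth |
|---|---|---|
| 6 | 1.6-13.8 | 2-46 |
| 12 | 1.3-7.5 | 6-66 |
| 24 | 1.15-4.3 | 15-80 |

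The spurious 6-versus-24 mg/kg half-life ratio is 1.4-3.2. With a 12-24 h fit the half-life maxima are 16.6, 8.9 and 5.0.

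**Rising endogenous level.** Put C(t) = 100 + 1.5t + (6/V)·exp(-kt). At V = 0.1 the fitted slope over 8-24 h is positive for all three half-lives, so half-life and AUC0-inf cannot be estimated. At V = 0.045 and 0.06 the slope stays negative and half-life is overstated.

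**Days 2 and 3, same-day subtraction.** Let f = exp(-24k) and let r be the residual drug in units of A: r = f on Day 2 and f + f² on Day 3. Drug AUC0-24 = (1 + r)(1 - f)/k; subtraction removes 24r. At 12 h, f = 0.25:

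- Day 2: r = 0.25, area 16.23; (16.23 - 6.00)/16.23 = 63%.
- Day 3: r = 0.3125, area 17.04; (17.04 - 7.50)/17.04 = 56%.

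At 8 h the recoveries are 74% and 71%; at 24 h, 54% and 41%.

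**The case against.** **The omission may be deliberate.** SAP 9.2 warns: "Geometric summary statistics will not be calculated for estimated rhu-pGSN concentrations, as these values could be lower than or equal to 0". A log-linear fit also fails at non-positive points, sampling ends at 24 h, and only one of the 12 h and 16 h samples is required. Simulation supports part of this. The assumptions were 6 mg/kg, true half-life 12 h, baseline 100 mg/L with log-SD 0.3, assay CV 5%, 8 placebo subjects and 4,000 runs per setting. With an endogenous rise of 1 mg/L/h (SD 0.5) and V = 0.1, pre-dose subtraction gave a median of 37 h (10th-90th percentile 13-181), with 32% not estimable. Double-delta gave 12.4 h (4.3-48.6), with 9% not estimable. This stands as a limit on precision and a reason to report both versions. It does not make total pGSN an estimate of rhu-pGSN, and the SAP uses the warning only to drop geometric summaries.

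**The protocol stores plasma "stored frozen for pGSN measurements" and prescribes no correction.** That is true of Protocol 11.4.3, but it describes the measurement and does not redefine the endpoint. The SAP already corrects the other parameters. A reader might infer that the tables pass total protein off as drug; they do not, since they are openly titled pGSN. The fault is a missing rhu-pGSN version.

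**Little depends on it.** Much of this stands. The trial is descriptive, escalation rests on Day 7 safety review, and corrected Day 1 Cmax, AUC0-t and AUC0-8 allow a check of dose proportionality. A reader might infer that rhu-pGSN PK as a whole, or the dose decisions, are compromised; the documents do not support that. SAP 1 would allow a later exploratory analysis, but labelled post hoc, which does not suit a named secondary endpoint.

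**Conclusion.** The plan is wrong as written for part of the secondary PK analysis and should be fixed. T1/2, AUC0-inf, k_el, %AUCext, CL/F, Vz/F and DN_AUC0-inf are planned on the wrong analyte for the stated endpoint. Tmax also lacks a rhu-pGSN version, with little consequence, since subtracting a constant leaves it unchanged.

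For a constant positive endogenous level the direction is firm: half-life and AUC0-inf upward, clearance downward, most at 6 mg/kg. A reader might extend that certainty to a rising level, but there the parameters are either biased upward or not estimable. No direction is claimed if the level falls during sampling.

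The size is unknown. The 1.15 to 14-fold range for half-life rests on assumed volume, half-life, baseline and fitting window. The upper extreme needs V = 0.1 L/kg, an 8 h half-life and a baseline of 200 mg/L, the bottom of the normal range, in patients whose levels are expected to be reduced. The Day 2-3 recoveries depend on the assumed half-life but not on dose, volume or baseline.

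**What to change.** **Day 1.** In SAP 9.1, SAP 9.2, Tables 14.2.3.x and Listings 16.2.6.4.x, add k_el, t1/2, AUC0-inf, %AUCext, CL, Vz, DN_AUC0-inf and, for completeness, Tmax on both planned corrected profiles. Name the main profile before unblinding and report the other as sensitivity. Leave non-positive corrected values out of the log-linear fit, require at least three positive terminal points, and report %AUCext and the number not estimable. Name the fitting window: a subject with only the 12 h or only the 16 h sample has three points from 8 to 24 h but only two from 12 to 24 h. Label the total-pGSN versions descriptive.

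**Declared change.** After a second dose, area to infinity includes drug from the first, so dose/AUC0-inf is not clearance. If AUC0-inf and CL are therefore limited to Day 1, record this in SAP 15, because Protocol 9.3 and 11.4.3 plan AUCinf for the first two multiple-dose administrations.

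**Days 2-3.** Also report corrected AUC0-t, AUC0-8 and Cmax against the Day 1 pre-dose, with and without placebo adjustment. Both are needed: under a rise of 1 mg/L/h at 6 mg/kg, V = 0.045 and a 12 h half-life, the unadjusted version would read 140% and 163% of drug AUC0-24 on Days 2 and 3. Make the SAP 3 baseline, the 9.1 rows (Cmax uses each day's pre-dose, DN_Cmax the Day 1 pre-dose), both 9.2 analyses and the MAD Listing 16.2.6.2.2 heading agree. The same heading in the single-dose listing is not a conflict.

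**Cost.** SAP text, shells and programming; no new samples. Some 6 mg/kg half-lives will be noisy or not estimable, and pre-dose subtraction is biased if endogenous pGSN rises. Placebo subjects number at most 8 on Day 1 and 6 on Day 2, possibly fewer on Day 3. Even a perfectly corrected AUC0-inf is extrapolated by 2^(-24/half-life): 13%, 25% and 50% at 8, 12 and 24 h.

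**Separate minor slip.** The DN_AUC0-8 row in SAP 9.1 divides AUC0-24 by dose; it should use AUC0-8, as in the SAP abbreviations list.
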